3.2 Sample Size

Up to 275 evaluable subjects will be enrolled in this study. Approximately 2 to 4 DLT-evaluable subjects will be enrolled in Cohort 1. Approximately 6 to 9 DLT-evaluable subjects will be enrolled in Cohort 2, Approximately 20 subjects will be enrolled each in Cohorts 3, 4 and 6, all outside of China. Approximately 12 subjects will be enrolled to Cohort 5 in China/Taiwan/Hong Kong. Approximately 40 subjects, respectively, will be enrolled to Cohort 7, Cohort 8 and Cohort 9. [REDACTED]

[REDACTED]

[REDACTED].

With 2 subjects in Cohort 1, there is a 36 – 55% probability of observing at least 1 DLT. With 4 subjects in Cohort 1, there is a 59 - 80% probability of observing at least 1 DLT if the true DLT rate is 20 – 33%.

[figure not shown]
Similarly, with 6 subjects per cohort, there is a 74 - 91% probability of observing at least 1 DLT. With 9 subjects per cohort, there is an 87 - 97% probability of observing at least 1 DLT if the true DLT rate is 20-33%.

In Cohorts 3, 4, 6, [REDACTED], a subject number of 20 will provide an 88% probability of observing at least one adverse event with 10% incident rate. An exact 80% binomial

confidence interval (CI) will be provided for overall response rate. With the 20 subjects and 25% overall response rate, the expected 80% CI would be 13% to 42%.

In Cohort 5, a subject number of 12 will provide a 72% probability of observing at least one adverse event with 10% incident rate. An exact 80% binomial confidence interval (CI) will be provided for overall response rate. With the 12 subjects and 25% overall response rate, the expected 80% CI would be 10% to 48%.

In Cohort 7, Cohort 8, and Cohort 9, the sample size is N~40 subjects. A subject number of N~40 subjects will provide an 87% probability of observing at least one adverse event with 5% incident rate. An exact 80% binomial confidence interval (CI) will be provided for overall response rate. With the 40 subjects and 25% overall response rate, the expected 80% CI would be 16% to 36%.

3.3 Adaptive Design

Dose level decisions are based on a modified toxicity probability interval design (mTPI). The mTPI was developed by [Ji et al. \(2010\)](#). The mTPI models the probability of toxicity for each dose level using a Bayesian model where each dose level has the same prior on the probability of toxicity, a Beta (1,1). When subjects are treated at the current dose level, the posterior probability of toxicity is updated using the observed data from this level. Dose level recommendation are made based on this posterior probability of toxicity, using three toxicity probability intervals (TPI).

- Under-dosing TPI: DLT rate from 0 to < 20%
- Target TPI: DLT rate from 20% to 33%
- Over-dosing: DLT rate > 33%

For the current dose level and after adjusting for the width of the under-dosing TPI, if the DLT rate is most likely in the under-dosing TPI then the recommendation is to dose escalate. If the DLT rate is most likely in the target TPI then the recommendation is to stay at the current level. If the DLT rate is most likely in the over-dosing TPI then the recommendation is to stop the enrollment. If DLTs are observed, the maximum tolerated dose (MTD) is the dose level with a DLT toxicity rate closest to 26.7% (Ji et al. 2010).

[figure not shown]
During enrollment and treatment at the RP2D using data from cohorts 3 and 6 and additionally using data from cohorts 7-9, objective response rate will be monitored with futility stopping rules described in [Section 7.1](#). These futility stopping rules are selected using practical considerations.

During enrollment and treatment at the RP2D using data from cohorts 3 and 6 and cohorts 7-9, subject incidence of grade 4 treatment related adverse events will be monitored with safety stopping rules described in [Section 7.1](#). The safety stopping rules use a Bayesian approach proposed by [Thall, Simon, and Estey \(1995\)](#) to terminate a cohort if the posterior probability that the subject incidence of grade 4 or higher treatment-related adverse events is greater than 20% is $> 80\%$. The stopping boundaries assume a prior distribution of Beta (0.40, 1.60).

4. Covariates [REDACTED]

4.1 Planned Covariates

The relationship of covariates to efficacy endpoints may be explored if appropriate.

5. Definitions

Adverse Event (AE)

An adverse event is any untoward medical occurrence in a clinical study subject irrespective of a causal relationship with the study treatment. An adverse event can therefore be any unfavorable and unintended sign (including an abnormal laboratory finding), symptom, or disease (new or exacerbated) temporally associated with the use of a treatment, combination product, medical device or procedure.

Age at enrollment

Subject age at enrollment will be determined using the age in years reported in the clinical database.

AUC

Area under the concentration-time curve reflects the actual body exposure to drug after administration of a dose of the drug ([M. Hidalgo et al](#)).

Baseline

For any variable, unless otherwise specified the baseline is the last non-missing assessment taken prior to the first administration of AMG 404. Where baseline measurements are taken on the same day as the study specified treatment and no times are present, it will be assumed that these measurements are taken prior to the study specified treatment being administered.

For parameters/assessments not scheduled to be performed (or scheduled but not performed) on the same day as the first administration of AMG 404, the baseline value is the value from the screening period measured closest to the day of first administration of AMG 404.

Baseline ECG Values in Triplicate

The baseline ECG is defined as the mean of the sets of triplicate screening ECGs and 1 set of triplicate ECGs obtained pre-dose on day 1; the mean of values in a triplicate should be calculated before taking the mean of the triplicate averages. When an ECG is missing within a triplicate, all available data will be averaged.

Bazett-corrected QT Interval (QTcB)

The Bazett correction will be calculated from the investigator reported QT (msec) and RR interval (msec), as follows: $QTcB = QT / (RR/1000)^{1/2}$.

Best Overall Response (BOR)

In general, the subject's best response assignment will depend on the findings of both target and non-target lesions and will also take into consideration the appearance of new lesions and confirmation of response.

Best overall response (BOR) will be based on all post-baseline disease assessments that occur prior to the initiation of subsequent anticancer treatment.

BOR for a subject is the best observed disease response per RECIST 1.1 in the following order: CR, PR, SD, PD, or NE. A best overall response of CR and PR require confirmation by a repeat, consecutive scan at least 4 weeks after the first documentation of response or progression.

A best overall response of SD requires an on-study imaging of SD or better no earlier than 7 weeks (49 days) after cycle 1 day 1.

Please refer [Appendix C](#) for deriving BOR algorithm as per RECIST 1.1.

Change from Baseline

Change from Baseline is the arithmetic difference between post-dose assessments and Baseline value.

Change (absolute) from Baseline = (Post-baseline Value – Baseline Value)

Change (percent) from Baseline = [(Post-baseline Value – Baseline Value)/Baseline Value] x 100

C_{max}

The maximum concentration of drug obtained in the serum.

Disease control rate

DCR is defined as the proportion of subjects in whom objective response (CR or PR) or stable disease (SD) is determined as per RECIST v1.1.

Dose Limiting Toxicity (DLT)

Defined as the severe toxicities during the first cycle of cancer therapy. A Dose Limiting Toxicity (DLT) is defined as any AE (meeting the criteria listed in section 8.4.2 of protocol) occurring during the first treatment cycle of AMG 404 (day 1 through day 28) where relationship to AMG 404 cannot be ruled out.

The DLT window (ie, DLT-evaluable period) will be the first 28 days of AMG 404 treatment (starting cycle 1, day 1).

Duration of Overall Response (DOR)

Duration of overall response is defined as the time from the first documentation of objective response, until the first documentation of disease progression, or death due to any cause, whichever occurs first. Only subjects who have achieved objective response will be evaluated for DOR. Duration of response will be censored as per PFS censoring rule.

Duration of Stable Disease (DoSD)

Duration of stable disease will be measured from the start of treatment until the first documentation of disease progression or death due to any cause. DoSD will be calculated only in subjects with best overall response SD.

Duration of stable disease will be censored as per PFS censoring rule.

End of treatment

Defined as the last assessment for the protocol specified treatment phase of the study for an individual subject.

End of Study

The end of study date is defined as the date when the last subject across all sites is assessed or receives an intervention for evaluation in the study (ie, last subject last visit), following any additional parts in the study (eg, long-term follow-up), as applicable.

End of Study for a particular subject

The end of study for a particular study subject will be the day of the last scheduled long term follow up (LTFU) call.

Enrollment

A subject is considered enrolled when the investigator decides that the subject has met all eligibility criteria (date eligibility worksheet been signed by investigator).

Fridericia-corrected QT Interval (QTcF)

The Fridericia correction will be calculated from the investigator reported QT (msec) and RR interval (msec), as follows:

[figure not shown]
$$QTcF = QT / (RR / 1000)^{0.33}$$

[figure not shown]
Investigational Product

The term investigational product is used in reference to AMG 404.

Last IP Dose Date

The last IP dose date for each subject is defined as the latest date IP is administered.

Long term follow-up visit

Long-term follow-up visit will be conducted 6 months (\pm 1 week) after the last dose of AMG 404.

Measurable baseline disease

Measurable baseline disease is defined as “Lesions must be accurately measured in at least one dimension (longest diameter in the plane of measurement is to be recorded) with a minimum size of 10 mm by CT scan or MRI. To be measurable a lymph node must be \geq 15mm in short axis when assessed by CT scan or MRI. All tumor measurements must be recorded in millimeters. Note: Previously irradiated lesions are non-measurable except in cases of documented progression of the lesion since the completion of radiation therapy.”

Objective Tumor Response

Objective response is defined as a tumor response assessment of either complete response (CR) or partial response (PR) measured by PET/CT, CT or MRI and assessed per RECIST v1.1. Subjects who do not experience PR/CR or do not have any follow-up tumor assessments will be regarded as non-responders. This endpoint will be determined only for subjects with measurable disease at baseline.

Overall Survival

Overall survival is defined as the time from the first dose of IP until death due to any cause. OS is censored at the last date known to be alive.

Primary Completion

The primary completion date is defined as the date when the last subject is assessed or receives an intervention for the final collection of data for the primary endpoint(s), for the purposes of conducting the primary analysis, whether the study concluded as planned in the protocol or was terminated early.

Progression Free Survival (PFS)

Progression-free survival is defined as the time from the first dose of IP until first documentation of radiological disease progression or death due to any cause, whichever occurs first. PFS will be censored at the last evaluable post-baseline tumor assessment date; otherwise, at first dose of IP. Progression will be based on RECIST v1.1.

Safety Follow-up visit

Upon permanent discontinuation from the study treatment for any reason, two safety follow-up visits are required. A safety follow-up visit will be performed approximately 30 (+3) days after the last administration of study drug, and also 140 days (± 7 days) after the last administration of AMG 404.

Serious Adverse Event

A serious adverse event (SAE) is defined as an adverse event that

- is fatal
- is life threatening (places the subject at immediate risk of death)
- requires in-patient hospitalization or prolongation of existing hospitalization
- results in persistent or significant disability/incapacity
- is a congenital anomaly/birth defect

- other medically important serious event

Study Day

Post study day: study day= (date - date of Study Day 1) + 1

Pre-study day: study day= (date – date of Study Day 1)

Study Day 1

It is defined as the first day that investigational product is administered to the subject. The day before Day 1 is referenced as Day -1.

t_{max}

The time takes to reach a maximum serum concentration of administered drug.

Treatment emergent AE

A treatment-emergent adverse event is any adverse event starting on or after the first administration of investigational product, as determined by the flag indicating if the AE started prior to first dose on the event eCRF and up to and including 140 days after the last IP dose date or end of the study, whichever occurs earlier.

Treatment related AE

A treatment-related adverse event is any treatment-emergent adverse event that per investigator review has a reasonable possibility of being caused by the investigational product. In the unlikely event that the relationship is missing, the treatment-emergent event will be considered treatment-related and documented in a footnote of the treatment-related summary.

6. Analysis Sets

The analysis of all endpoints, unless noted otherwise, will be conducted on the Safety Analysis Set.

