9.5.2 Analyses of Secondary Efficacy Endpoint(s)

For all subjects treated at the RP2D and separately by cohort, the following analyses will be done. The proportion of subjects with confirmed objective tumor response (partial and complete response) and disease control rate (DCR) (partial or complete control) with corresponding exact 80% CI will be calculated and tabulated. Similarly, the proportion of subjects and 80% CI will be tabulated for 1-year duration of overall response, 1-year PFS, 1-year duration of stable disease and 1-year OS. Kaplan-Meier curve will be presented for duration of overall response, PFS, OS and duration of stable disease with estimates for rate and 80% CI at selected weeks based on the Brookmeyer and Crowley method ([Brookmeyer & Crowley, 1982](#)) if data allows.

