Appendix C. BOR per RECIST (v1.1) Criteria

The protocol requires that a PD must be confirmed. The analysis of modified RECIST 1.1 BOR endpoints will follow standard RECIST 1.1 convention which does not require confirmation of PD.

Best Overall Response (BOR) determination per RECIST 1.1 is given in below in [Table 14-2](#), the BOR considered is a Confirmed BOR.

Table 14-2. BOR per RECIST 1.1

Criterion	Time point T1 Response	T1 ≥ 49 days after C1D1?	Time point T2 Response	T2 ≥ 49 days after C1D1?	T2 ≥ 28 days after T1?	BOR	
C1	CR	Yes	CR	-	Yes	CR	
C2			CR	-	No	SD	
C3		No	-	PR, SD	-	-	Query data*
C4				PD	-	-	SD
C5				NE, No further evaluations			SD
C6				CR	-	Yes	CR
C7				CR	Yes	No	SD
C8				PR, SD	-	-	Query data*
C9		PD	-	-	PD		
C10		NE, No further evaluations			NE		
C11	PR	Yes	CR, PR	-	Yes	PR	
C12			CR, PR	-	No	SD	
C13		No	-	SD	-	-	SD
C14				PD	-	-	SD
C15				NE, No further evaluations			SD
C16				CR, PR	-	Yes	PR
C17				CR, PR	Yes	No	SD
C18				SD	Yes	-	SD
C19		PD	-	-	PD		
C20		NE, No further evaluations			NE		
C21	SD	Yes	CR, PR, SD, PD, NE, no more evaluation			SD	
C22			CR, PR, SD	Yes	-	SD	
C23		No	-	CR, PR, SD	No	-	NE
C24				PD	-	-	PD
C25				NE, No further Evaluations			NE
C26	PD	-	-	-	-	PD	
C27	NE	-	NE, No further evaluations			NE	
C28		-	CR, PR, SD	Yes	-	SD	
C29		-	CR, PR, SD	No	-	NE	
C30		-	PD	-	-	PD	

CR = complete response, PR = partial response, SD = stable disease, PD = progressive disease, and NE = not evaluable.

*If a CR is truly met at first time point, then any disease seen at a subsequent time point, even disease meeting PR criteria relative to baseline, makes the disease PD at that point (since disease must have reappeared after CR). Best response would depend on whether minimum duration for SD was met. However, sometimes 'CR' may be claimed when subsequent scans suggest small lesions were likely still present and in fact the patient had PR, not CR at the first time point. Under these circumstances, the original CR should be changed to PR and the best response is PR.

A CR must be confirmed by CR, a PR can be confirmed by a PR or CR.

An unlimited number of intermittent assessments of NE can occur between the initial response and the confirmation. For example, BL, CR, NE, NE, NE, CR – the CR at post baseline 1 is confirmed at post baseline 5.

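### As worded, the SAP does not limit duration of response to confirmed responders, so read literally one subject can be an ORR non-responder and still count in both DOR and duration of stable disease

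*SAP*

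**What the plan says.** All the definitions are in SAP Section 5 unless another place is given.

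- **DOR, start:** "Duration of overall response is defined as the time from the first documentation of objective response".
- **DOR, who is included:** "Only subjects who have achieved objective response will be evaluated for DOR".
- **Objective response:** "Objective response is defined as a tumor response assessment of either complete response (CR) or partial response (PR) measured by PET/CT, CT or MRI". The entry treats as non-responders those who never show PR or CR and those without follow-up scans. It does not mention subjects whose response was not confirmed.
- **Duration of stable disease (DoSD):** "DoSD will be calculated only in subjects with best overall response SD".
- **BOR:** "A best overall response of CR and PR require confirmation by a repeat, consecutive scan at least 4 weeks after the first documentation". Appendix C repeats this for Table 14-2: "the BOR considered is a Confirmed BOR".
- **Response rate, SAP 9.5.2:** "The proportion of subjects with confirmed objective tumor response (partial and complete response" is tabulated with an exact 80% CI. The sentences on 1-year DOR and the DOR curve do not repeat the word confirmed.
- **Protocol:** 10.2.2 requires CR and PR to be confirmed by a further scan at least 4 weeks later. The best-response table in Appendix 10 is also headed as requiring confirmation. The same appendix starts DOR when CR or PR criteria are first met.

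**The concern.** DOR and DoSD select subjects on different definitions. DoSD uses BOR, which is confirmed. DOR uses objective response, whose own definition is satisfied by a CR or PR assessment with no repeat scan. The word confirmed appears in 9.5.2 for the response proportion only. A programmer who follows Section 5 to the letter would put unconfirmed responders into DOR. One who reads it together with the protocol would not. Both would be acting in good faith, and their DOR tables would differ.

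Under the literal reading, DOR describes a wider group than the responders counted in ORR. Some of its members also appear in the DoSD curve. Those who progress at the next scan have about the shortest DOR that an 8-week schedule can record. The numbers are small: at the SAP's illustrative 25% response rate, a cohort of 20 to 40 has 5 to 10 responders. One extra subject would then be 1 in 6 to 1 in 11 of the DOR set.

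**Working it through.** **1. The plan's own figure.** SAP 3.2 gives an expected exact 80% CI of 16% to 36% for 40 subjects at a 25% response rate, that is x = 10, n = 40. By Clopper-Pearson:

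- lower limit = 10th percentile of Beta(10, 31) = 16.2%
- upper limit = 90th percentile of Beta(11, 30) = 35.9%

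The figure reproduces. It rests on the response count alone, so the DOR wording does not affect it.

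**2. What selects subjects for each analysis.**

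| Analysis | Selected on | Confirmation stated? |
|---|---|---|
| ORR (SAP 9.5.2) | CR or PR | Yes |
| DoSD (Section 5) | BOR = SD | Yes, through confirmed BOR |
| DOR (Section 5) | Objective response | No |
| Futility count (SAP 7.1) | Objective response per RECIST 1.1 | No |

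**3. One subject followed through.** Scans are every 8 (±1) weeks (protocol Table 3-1, footnote 5), so an on-schedule first scan falls between day 7 × 7 = 49 and day 9 × 7 = 63. That meets the 49-day condition in Table 14-2. Take PR on day 56 and PD on day 112, which is row C14:

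- BOR = SD, so the subject is a non-responder for ORR.
- DOR under the literal Section 5 wording: 112 − 56 = 56 days, about 8 weeks.
- DoSD, counted from the start of treatment: 112 days, about 16 weeks.

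Appendix C analyses PD without requiring its confirmation, so the day-112 scan ends both durations.

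**4. How many rows of Table 14-2 allow this.** The two rows sent for data query (C3, C8) are left out.

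- Confirmed CR or PR: C1, C6, C11, C16 (4 rows).
- A CR or PR can be present but the row gives SD: C2, C4, C5, C7, C12 to C15, C17, C18, C21, C22, C28 (13 rows).
- A CR or PR can be present but the row gives PD or NE: C9, C10, C19, C20, C23, C29 (6 rows).

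Each row describes a pair of scans, so some of these responses could still be confirmed at a later scan under another row. If DOR is restricted to a BOR of CR or PR, only the first group feeds it and the overlap with DoSD is zero.

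**5. Direction of the effect, by row.**

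- C14 (PR, then PD): a short DOR event, which lowers the estimates.
- C13 (PR, then SD): DOR runs until progression or death and may be long.
- C12 (second CR or PR less than 28 days later): may also be long.
- C15 (PR, then not evaluable or no further scans): under the PFS censoring rule the subject is censored at the last evaluable scan, so adds almost no follow-up unless a death is recorded.

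**6. Illustration of size.** None of these inputs is in the documents. Assume 40 subjects, 10 confirmed responders, no censoring, and 2 or 4 unconfirmed responders who all progress at the next scan. ORR is 10/40 = 25% throughout.

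| Confirmed responders still responding at 1 year | No unconfirmed | 2 unconfirmed | 4 unconfirmed |
|---|---|---|---|
| 5 of 10 | 5/10 = 50% | 5/12 = 42% | 5/14 = 36% |
| 7 of 10 | 7/10 = 70% | 7/12 = 58% | 7/14 = 50% |

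**The case against.** The strongest reply is that the documents, read together, already mean confirmed response. Protocol 10.2.2 requires confirmation, and Appendix 10 of the protocol heads its best-response table the same way. The SAP says it details the analyses outlined in protocol amendment 6. BOR is confirmed throughout the SAP, and 9.5.2 analyses confirmed response and then turns to the durations as a similar analysis. On this view the phrase about first documentation only fixes the start date and does not define the population.

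Much of this stands. Confirmed responders were probably intended, and on that reading there is no double counting. A reader might infer that the SAP deliberately includes unconfirmed responders. It does not: no sentence says so, and the point is that the wording fails to exclude them. A reader might also infer that DOR will be biased downward. The documents do not support that in general, because rows C12, C13 and C15 need not shorten it, and no rate of unconfirmed response is given. Nor do the documents themselves describe DOR and DoSD as mutually exclusive.

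The reply does not remove the conflict. Section 5 defines the term that selects the DOR set, and that definition has no confirmation condition. The protocol's own DOR entry does not supply one. Its accompanying note on confirmation refers to trials with response as the primary endpoint, which is not the case here.

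**Conclusion.** The concern holds as a wording defect. Taken literally, the SAP's definitions give a result at odds with its own confirmed ORR and confirmed BOR, and with the protocol's confirmation rule: an unconfirmed responder in row C14 counts against ORR but enters both DOR and DoSD. Unconfirmed responders who progress or die early would lower the DOR curve and the 1-year rate. Others would not necessarily do so.

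The effect cannot be sized from the documents. The fall from 50% to between 42% and 36% depends on the assumed counts, on every unconfirmed responder progressing at the next scan, and on no censoring. DOR is a secondary, descriptive endpoint in a study whose primary endpoints are safety. No hypothesis, sample size, stopping boundary or dose decision depends on it, and ORR is unaffected.

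**What to change.** In the DOR entry of SAP Section 5, state that DOR is evaluated only in subjects with a confirmed BOR of CR or PR per Table 14-2, measured from the first scan that shows the response later confirmed. Unconfirmed responders then belong only to the BOR category that Table 14-2 assigns them. State the same confirmed definition for the ORR analysis in 9.5.2.

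Do not do this by redefining objective response throughout the SAP without comment. The futility rule in SAP 7.1 counts objective responses once 15 and 25 subjects have been treated for at least 3 months, and does not say whether they must be confirmed. With scans at about weeks 8 and 16, a response first seen at week 8 may still be unconfirmed at 3 months (about week 13), since protocol 10.2.2 lets confirmation wait for the next scheduled scan. A blanket change could therefore alter that count. Section 7.1 should keep its own stated definition.

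The cost is SAP wording only, with no new data and no protocol amendment. The downside is a slightly smaller DOR set.
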